All subjects will receive antibiotics intravenously for at least 2 days postoperative or until they are able to tolerate oral/enteric feedings. Intravenous antibiotics are routinely used postoperatively at ChiLDREN centers as prophylaxis against ascending cholangitis. The choice of antibiotics will be according to the local standard of care. Once oral/enteric feedings are tolerated, oral trimethoprim-sulfamethoxazole (TMP/SMZ, 4-5 mg TMP/kg/day) will be initiated and continued for 6 months. In the event of the occurrence of an episode of cholangitis despite antimicrobial prophylaxis, subjects will be treated with parenteral antibiotics according to the standard of care at the clinical center where the subject is enrolled. Thereafter, prophylaxis with oral TMP/SMZ will be used for 6 months. In addition to serving as prophylaxis against ascending cholangitis for all subjects⁵⁴, this regimen will also provide prophylaxis for pneumocystis carinii pneumonia (PCP) in subjects receiving corticosteroids. In the unlikely event that the subject develops a hypersensitivity reaction to TMP/SMZ manifested as a skin rash (see section 7.D8), the medication will be discontinued promptly and the subject will undergo a blinded taper and discontinuation of the study drug/placebo as outlined in Section 4.F3.

4.H. Follow-up Study Visits for this Clinical Trial

Following portoenterostomy and discharge from the hospital, subjects will be evaluated in the outpatient clinic 2 weeks after portoenterostomy, at 1, 2, 3, and 6 months after portoenterostomy, and then at 12, 18, and 24 months of age. The inclusion of the 2-week time point will allow for careful monitoring for side effects of corticosteroid treatment. During each outpatient visit, information will be recorded on ChiLDREN Case Report Forms (CRFs), which are the same forms used in the ChiLDREN prospective observational database protocol, and on additional forms that collect information that is specific for this trial. These forms will capture data on the subject's physical findings, diet and medication records, laboratory findings, interval medical history, interval sentinel events, illnesses or hospital admissions, surgery, imaging follow-up, pathology, HRQOL, and antibody titers to vaccines according to the schedule in Table 6 (below).

Table 6. Schedule of Evaluations for the Trial of Corticosteroid Therapy in Infants with Biliary Atresia.

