Evaluation	Recruitment or Baseline	Diagnosis/ Surgery/ Discharge	2 wk post	1,2,3 & 6 m post Kasai	12 m age	18 m age	24 m age	At transplant
Windows for visits			±1 wk	±2wks; ±4 wks for 6 m	±1 mo	±2 mo	±2 mo	
Inf. Consent & eligibility	X							
Intake/Medical History	X		X	X	X	X	X	X
Diagnosis and surgery		X						
Discharge Assessment		X						
Medication Record	X	X	X	X	X	X	X	X
Physical Exam, Growth Measures	X	X	X	X	X	X	X	X
Blood tests -Complete blood count -LFTs, PT/INR -Electrolytes, creatinine, BUN, glucose	X	X	X	X	X	X	X	X
Blood tests -Retinol, RBP, 25OH-VitD -Vitamin E, total lipids -Bile acid, PIVKA-II				X*	X	X**	X	
Interval Medical History			X	X	X	X	X	X
Interval Sentinel Events			X	X	X	X	X	X
Neurodevelopmental Assessment (Bayley)					X		X	
Health-Related Quality of Life Inventory (HRQOL)					X		X	
Ophthalmological exam					X			
Antibody titers to vaccines						X		

*Will not be done at the 2 month follow-up, unless a dose adjustment was performed at the 4 week follow-up.

**Will be done only if infant still requires AquADEK® to maintain adequate serum levels of fat-soluble vitamins.

4.I. Surgical procedures and Laboratory Tests

Results of surgical procedure(s) and laboratory tests performed for the initial diagnosis of biliary atresia will be obtained from the medical records. These tests will include hematologic and biochemical analysis (such as complete blood count, liver function tests, prothrombin time/INR, urinalysis, etc), imaging (such as ultrasound examination and hepatobiliary scan), and results of hepatobiliary pathology. Results for tests done at the time of hospital discharge following portoenterostomy will also be obtained from the medical records. Following discharge, the following laboratory tests will be obtained in all subjects, at the time points shown in Table 6, in order to assess study outcomes: liver function tests, complete blood count, vitamin levels and prothrombin time. Serum electrolytes and glucose will also be measured to monitor for potential adverse effects of corticosteroid treatment. These laboratory tests will be performed using standard automated assays in certified clinical laboratories located at each ChiLDREN clinical center.

4.J. Preparation and Administration of Study Medication and Placebo

4.J1. Preparation, Packaging, and Labeling

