- AquADEK® and vitamin K (Mephyton®) (up to two years)
- Ursodeoxycholic acid (Urso 250® or Actigall®) (up to two years)
- TMP/SMZ (up to six months)
- Ranitidine (Zantac®) (up to three months while the masked study medication is being prescribed)

4.K. Adherence to protocol and withdrawal from the study

4.K1. Adherence to Protocol

Every effort will be made by study personnel to ensure adherence to the protocol by study subjects and their families. This includes enrollment of all eligible subjects, prompt randomization to the study drug or placebo, and initiation of data collection in a timely manner. All interactions with the study subjects and their caregivers will be performed by the same personnel utilizing supportive and positive reinforcement communication skills, and will include direct feedback regarding amount of unused medication. Compliance will be assessed by the site research coordinator by reviewing the medication bottles. To this end, parents will be asked to bring the previously dispensed study drug/placebo to each follow-up visit so that compliance can be estimated by the difference between the actual and the expected volumes remaining in the drug/placebo container.

4.K2. Subject Withdrawal from Study

It is the right of the subject's parents, or guardians, or the primary care providers caring for each subject to withdraw the subject from the study and wean (taper) the study drug/placebo at any time during the study. Subjects will be removed from the study for any of the following reasons:

- Withdrawal of consent.
- Subject is lost to follow-up. If a subject fails to appear for scheduled appointments, the research coordinator will call the parents/guardians by phone. If the family does not respond or cannot be located, a certified letter will be mailed to the parents/guardians asking them to immediately contact the clinical center.

Any subject who withdraws from the study will undergo the drug/placebo taper protocol described in Section 4.F3, and will receive standard medical care.

If the attrition rate is greater than 20%, the sample size may be adjusted.

4.K3. Discontinuation of Study Drug/Placebo

Study drug/placebo will be discontinued (see Section 4.F3), however subjects will continue to be followed for the duration of this study, if:

- The investigator believes it is no longer in the best interest of the subject to remain in the study.

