- There is a serious adverse event, as outlined in the Data and Safety Monitoring Plan (Section 7).

Any subject who is withdrawn from the study drug/placebo will undergo the drug/placebo taper protocol described in Section 4.F3, and will receive standard medical care.

All subjects will continue to be followed per protocol even if the study drug/placebo is tapered and/or discontinued.

4.L. Retention of Participants

Special effort will be made to keep attrition of study subjects below 20% using the following methods:

- Some of the costs associated with provision of care (such as laboratory tests) will be covered by this study. Thus, we expect minimal attrition due to financial constraints.
- The study coordinator will provide assistance to the parents/legal guardians of study participants, such as scheduling of appointments. Thus, we would make an effort to minimize attrition due to logistical considerations.

4.M. Routine Clinical Care Guidelines for ChiLDREN

Routine clinical care guidelines were established for infants enrolled in the ChiLDREN prospective database and will be followed in this clinical trial. These guidelines were developed based on a consensus of the ChiLDREN clinical investigators in regard to optimal medical and nutritional management and the frequency of follow-up visits for infants with biliary atresia.

4.M1. Frequency of Medical Encounters/Visits

- Enrollment and initial evaluation
- Discharge from the hospital
- 2 weeks postoperative, 1, 2, 3 and 6 months post-operative, and 12, 18 and 24 months of age. The visit at 12 months of age may be combined with the 6-month postoperative visit when the latter is at 10 months of age or greater (which can happen if the portoenterostomy is performed at 4 months of age or later)
- Annually thereafter

4.M2. Physical Exam

At each medical encounter/visit, the following will be obtained:

- Height or recumbent length, weight, head circumference, triceps skinfold thickness, mid-arm circumference.
- Vital signs.
- Skin examination for jaundice, xanthomas, palmar erythema, and vascular pattern.
- Abdomen examination to determine liver size and texture, spleen size, ascites.
- Examination of extremities for edema and clubbing.

4.M3. Diet

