When the total bilirubin is ≥ 1.5 mg/dL and the child is less than 12 months of age, MCT-containing formula or breast milk should be used, as long as the child's growth is "adequate". When the total bilirubin is < 1.5 mg/dL, the child can be transitioned to standard infant formula (if < 1 year of age) and whole milk (if ≥ 1 year of age). MCT-containing formula will be continued until 24 months of age if the total bilirubin is ≥ 1.5 mg/dL and the child is over 12 months of age. When growth is inadequate, measures will be taken for nutritional rehabilitation according to medical management used at each ChiLDREN clinical center.

4.M4. Vitamin Supplementation

All cholestatic subjects with total bilirubin ≥ 1.5 mg/dL will receive:

- AquADEK® vitamin drops: 2 ml orally per day until 2 years of age
- Vitamin K : 2.5 mg orally coadministered with AquADEK® vitamin drops on Mondays, Wednesdays and Fridays

AquADEK® and Vitamin K may be stopped when the total bilirubin is < 1.5 mg/dL. Serum vitamin levels and prothrombin time/INR will be measured during the follow-up visit at one month after portoenterostomy. When an abnormal value is obtained, the dosage of the specific vitamin will be augmented or reduced, as appropriate, and the level will be rechecked in 4 weeks (see Section 4N, below).

4.M5. Ursodeoxycholic Acid

- Ursodeoxycholic acid (Urso 250® or Actigall®): 20 mg/kg/day divided BID orally until 2 years of age.

Ursodeoxycholic acid will be discontinued if serum total bilirubin is > 15 mg/dL to avoid potential toxicity.

4.M6. Antibiotics for Prophylaxis Against Ascending Cholangitis

- TMP/SMZ: 4-5 mg TMP/kg/day orally for 6 months

If the subject has evidence of decreased renal function as indicated by an elevated serum level of creatinine, we will adjust the dose of TMP/SMZ for renal insufficiency. For serum creatinine > 1.0 to 1.5 mg/dL, the dose will be reduced by 25%; for creatinine > 1.5 to 2.5 mg/dL, the dose will be reduced by 50%; and for serum creatinine > 2.5 , the subject will be withdrawn from the study. These adjustments are based on a normal serum creatinine of < 0.6 mg/dL in the first year of life.

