If the subject develops a hypersensitivity reaction to TMP/SMZ manifested by a skin rash, the medication will be discontinued promptly and oral neomycin (25 mg/kg PO twice daily) will be used as prophylaxis against ascending cholangitis. Because neomycin provides no prophylaxis against PCP, the subject will also undergo a blinded taper. The study medication will be discontinued as outlined in (Section 4.F3) and the subject will continue to be followed per protocol even when off medication. Our choice to discontinue the study drug/placebo is based on concerns of the risk of PCP in the immunocompromised infant without TMP/SMZ prophylaxis.

7.D9. Cataracts

Cataracts are a well-recognized complication of long-term corticosteroid therapy, and are related both to dosage and duration of therapy. Children appear to be particularly at risk for steroid-induced cataracts. Despite the relative short duration of corticosteroid treatment in this clinical trial, all subjects will undergo an ophthalmologic examination at 12 months of age to monitor for the development of corticosteroid-induced posterior subcapsular cataracts. The examination will be performed by a pediatric ophthalmologist. The incidence of cataracts in corticosteroid treated-subjects and in placebo controls will be reported to the DSMB.

7.E. Vitamin Toxicity Monitoring

There is a potential risk of vitamin toxicity from supplementation. However, specific toxic concentrations of each of the fat-soluble vitamins are not available in the literature. Therefore, close monitoring of vitamin levels to confirm that they are not above the normal ranges reported by the laboratory is planned and outlined in section 4.N8 and 4.N9. Fat-soluble vitamin status will be checked within one month after starting supplementation through routine testing. Whenever a vitamin dose adjustment is made, follow-up testing will be performed within one month. If there is a major or rapid change in the severity of cholestasis (e.g., rapidly decreasing levels of serum bilirubin), vitamin levels will be monitored more frequently.

7.F. Adrenal Insufficiency:

During the taper: In the event of a life-threatening complication and when the physician treating the subject determines that knowing whether the subject was taking

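### Section 4.M6 withdraws infants with serum creatinine above 2.5 mg/dL from the study, although Sections 4.K3 and 7.D8 stop medication but keep follow-up

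*Protocol*

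**What the plan says.** Section 4.M6 gives oral TMP/SMZ for 6 months and adjusts it for renal function. The dose falls by 25% for creatinine above 1.0 up to 1.5 mg/dL and by 50% above 1.5 up to 2.5 mg/dL. For the step above 2.5 the text is "the subject will be withdrawn from the study. These adjustments are based on a normal serum creatinine", and the normal value is put at below 0.6 mg/dL in the first year. The sentence does not say that TMP/SMZ is stopped.

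Other sections handle participation differently:

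- Section 4.K2 lists two reasons for removal from the study: withdrawal of consent and loss to follow-up.
- Section 4.K3 covers stopping study drug, "however subjects will continue to be followed for the duration of this study". One trigger is "The investigator believes it is no longer in the best interest of the subject to remain in the study"; the other is a serious adverse event. It closes with "All subjects will continue to be followed per protocol even if the study drug/placebo is tapered and/or discontinued".
- Section 7.D8, on TMP/SMZ hypersensitivity, replaces TMP/SMZ with neomycin, tapers study drug, and adds that "the subject will continue to be followed per protocol even when off medication".
- Section 5.A.1 places all randomized subjects in an intent-to-treat analysis and defines attrition as withdrawal by parents or guardians, including loss to follow-up, in the first 6 months.

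On timing, Section 4.G says oral TMP/SMZ "will be initiated and continued for 6 months", and after a cholangitis episode: "Thereafter, prophylaxis with oral TMP/SMZ will be used for 6 months". Study drug lasts 13 weeks (Section 6.A3). The Table 6 row containing "Electrolytes, creatinine, BUN, glucose" is marked at every visit.

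**The concern.** A dose rule for a supportive antibiotic ends with a randomized infant leaving the trial. The trigger arises after randomization and marks a sick infant, so any outcome lost this way is unlikely to be lost at random. The removal is ordered by the protocol and not chosen by the family, so it falls outside both the removal list in 4.K2 and the attrition definition in 5.A.1.

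After week 13, removal cannot reduce steroid exposure, yet it can still come before the 6-month bilirubin measurement. If TMP/SMZ is restarted after cholangitis, the rule can also act later and end trial follow-up for the 24-month outcomes.

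**Working it through.** **1. The texts side by side.**

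| Situation | TMP/SMZ | Study drug | Follow-up |
|---|---|---|---|
| Creatinine >2.5 (4.M6) | not stated | tapered, as for any withdrawal (4.K2, 4.F3) | ends |
| TMP/SMZ hypersensitivity (4.M6, 7.D8) | stopped, neomycin instead | tapered and stopped | continues |
| Investigator judges that staying in is not in the infant's interest (4.K3) | – | tapered and stopped | continues |
| Serious adverse event (4.K3) | – | tapered and stopped | continues |

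The first row is the exception, and the protocol gives no reason for it. Section 4.B also removes infants, but only those found not to have biliary atresia.

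**2. Exposure window.** Study drug lasts 13 × 7 = 91 days. Six months of TMP/SMZ is about 183 days. If both start soon after surgery, 183 − 91 = 92 days, or 92/183 = 50% of the TMP/SMZ course, fall after study drug has ended and before or around the 6-month endpoint.

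**3. The plan's own sample size.** Section 5.A.1 states 110 subjects for 50% versus 75%, 80% power and two-sided 5%. With unpooled variance, n per arm = (1.96 + 0.8416)² × (0.50×0.50 + 0.75×0.25) / 0.25² = 54.9, so 55 per arm and 110 in total, as stated. The final target is 140, or 70 per arm.

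**4. Loss of numbers.** The protocol gives no rate of creatinine >2.5, so I assume 1 to 7 of 140 (0.7% to 5%). Power by the pooled formula is Φ{[0.25√n − 1.96√(2×0.625×0.375)] / √0.4375}:

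- n = 70 per arm: 87.2%
- n = 69.5 (one lost): 86.9%
- n = 66.5 (seven lost): 85.4%

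The loss of numbers hardly matters.

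**5. Selective loss.** Assume 70 per arm, true rates of 50% (35/70) and 75% (52.5/70), that every removed infant would have been a failure, and that the 6-month outcome stays missing and is left out of the rate. Removing k failures from an arm gives 35/(70−k) or 52.5/(70−k):

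- k = 1: 35/69 = 50.7%; 52.5/69 = 76.1%
- k = 3: 35/67 = 52.2%; 52.5/67 = 78.4%

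| Removed | Difference, k = 1 | Difference, k = 3 |
|---|---|---|
| none | 25.0 | 25.0 |
| k in each arm | 25.4 | 26.1 |
| k in steroid arm only | 26.1 | 28.4 |
| k in placebo arm only | 24.3 | 22.8 |

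For scale, the standard error of the difference is √[(0.25 + 0.1875)/70] = 7.9 points. The largest shift shown, 28.4 − 25.0 = 3.4 points, is less than half of that.

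**6. What could be recovered.** Table 9 marks the 6-month visit and liver function tests as database and clinical-care items. Section 3.A5 has the database following infants at 18 and 24 months of age. The vitamin A, D and E markers are marked as clinical care and trial. Bile acids, PIVKA-II and vaccine titers are marked as trial only. Section 7.B1 continues adverse-event evaluation after withdrawal.

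**The case against.** The strongest reply is that this is a slip of one phrase with little consequence.

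- Section 5.A.1 expects withdrawals and still promises an intent-to-treat analysis, so withdrawal does not by itself remove anyone from the analysis set. Section 5.B allows imputation. This stands: 5.A.1 is not strictly contradicted. The rule still creates avoidable missing data in that analysis.
- 4.K3 is about stopping study drug, 7.D8 concerns a different event, and 4.B shows that the 4.K2 list is not exhaustive, so 4.M6 could be a further specific exception. But no reason is given for it, and 4.K3 keeps follow-up even when the investigator doubts that participation serves the infant.
- A creatinine this high may qualify as a serious adverse event under 7.B3, and 4.K3 would then keep follow-up. That leaves a site with two opposite instructions; it does not settle which applies.
- The later reach of the rule rests on 4.G, while 4.M6 says 6 months and 4.J4 supplies TMP/SMZ for up to six. This is fair; that part of the concern is secondary.
- The vitamin A, D and E markers are also clinical care, and the items collected only by the trial bear on tertiary outcomes. This limits the loss. Clinical-care results still do not reach the trial automatically once an infant has left it.
- The shifts in step 5 need every removed infant to be a failure and to be dropped as missing. They are a range under stated assumptions and do not predict what will happen.

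Reading the phrase as withdrawal from study drug would not cure it: the sentence would still not stop TMP/SMZ, and it would have no effect after week 13.

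**Conclusion.** The concern holds. As written, 4.M6 ends trial follow-up for an illness-related reason, against 4.K2 and 4.K3 and out of line with 7.D8.

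It is minor. The number affected is unknown and probably very small: the trigger is more than four times the stated normal limit (2.5/0.6 = 4.2), and severe renal disorders that would interfere with the study are excluded at entry. Under the assumptions shown, the primary difference would move by 0.4 points for one infant per arm and by up to 3.4 points for three in one arm. It would not move if 6-month status is recovered from the database, or if the infant already counts as a failure through transplant or death. Recovery depends on database consent remaining usable after trial withdrawal, which the protocol does not spell out.

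**What to change.** Replace the last step of the 4.M6 ladder with wording such as:

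*For serum creatinine >2.5 mg/dL, TMP/SMZ is stopped, other cholangitis prophylaxis is given by local standard of care as renal function allows, and study drug/placebo, if still being given, is tapered and stopped under Section 4.F3. The infant remains in follow-up on the protocol schedule.*

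Also state that, where consent allows, the database's 6-month bilirubin and native-liver status will be used for any infant who leaves only the trial.

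The cost is one sentence in 4.M6, one on use of database results, and a check of the consent wording. No visits or tests are added.
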